5.3.1 Assessments

The following will be completed during each follow-up Cytosponge administration

- Re-affirmation of consent
- Cytosponge administration
- Visual Analog Scale
- Adverse event assessment
- Routine care upper endoscopy with biopsy
- Follow-Up Case Report Form (CRF): This captures demographics including race, ethnicity, gender, and year of birth, relevant EoE medical history since enrollment including documentation of endoscopic procedures received, pathology findings and EoE treatment(s) received since enrollment.

5.4 Follow-Up Phone Call

Subjects will be contacted 7 days (+/- 2 days) after the follow-up Cytosponge and upper endoscopy procedures. During this phone call, adverse events will be assessed and subjects will complete questionnaires. The same assessments are completed during the follow-up phone call following a follow-up Cytosponge administration as were completed during the initial Cytosponge administration. See section 5.2 for details.

5.5 Subject Participation Completion

Subject participation is considered complete when the subject no longer returns to the enrolling site for clinical care of their condition, or prior to that time if the subject withdraws for any reason (see section 4.4).

6 Statistical Plan

6.1 Sample Size Determination

With 60 subjects enrolled for Aim 1, we will be able to detect a correlation between the Cytosponge and endoscopy eosinophil counts as low as $R = 0.40$ with a power of 0.9 and an alpha of 0.05. This sample size would also have a power of 0.8 to detect an agreement (kappa) of as low as 0.7 (compared to a null of 0.4).

We will allow for enrollment up to 150 subjects across both sites to account for any potential issues with sample quality and additional safety assessments.

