Diagnosis and monitoring of eosinophilic esophagitis using the Cytosponge

NCT02114606

Protocol Version Date:

25 September 2020

DIAGNOSIS AND MONITORING OF EOSINOPHILIC ESOPHAGITIS USING THE CYTOSPONGE

Principal Investigator

[name], MPH
Assistant Professor of Medicine and Epidemiology
University of North Carolina School of Medicine
[name]
[name]
[contact]

Co-Investigators

[name]
Mayo Clinic Rochester
Rochester, MN

[name], MA, MD
Cambridge University
Cambridge, U.K.

[name], MPH
University of North Carolina School of Medicine
Chapel Hill, NC

Funding Sponsor:

CURED (Campaign Urging Research for Eosinophilic Disease) Foundation

UNC IRB Number:

13-3521

Protocol Version:

4.0

Protocol Version Date:

25 September 2020

SIGNATURE PAGE

The signature below constitutes the approval of this protocol and the attachments, and provides the necessary assurances that this trial will be conducted according to all stipulations of the protocol, including all statements regarding confidentiality, and according to local legal and regulatory requirements and applicable US federal regulations and ICH guidelines.

Principal Investigator or Clinical Site Investigator:

Signed:

Date:

Name:

Title:

Summary of Changes

Version 4.0 dated 25Sep2020	
Study Summary	Objectives and methodology updated according to changes made to these sections of the protocol.
2.0 Study Objectives	Aim 2 removed as the scope of the study was limited by device availability and aim 2 was unable to be evaluated with available data.
3.1 General Design	Reference to Aim 2 removed.
3.4 Secondary Outcomes	Added “agreement between cytosponge and endoscopic biopsy as measured by kappa.” Revised secondary outcome to clarify measures used to assess acceptability.
6.1 Sample Size Determination	Removed reference to Aim 2.
6.2 Statistical Methods	Removed reference to Aim 2.
Administrative Changes	Administrative changes to protocol version and version dates throughout.
Version 3.0 dated 05Sep2017	
3.1 General Design	Additional analyses on samples has been added.
Administrative Changes	Administrative changes to protocol version and version dates throughout as well as updating table of contents and section numbers.
Version 2.0 dated 05Oct2016	
Study Summary 6.1 Sample Size Determination	Increased enrollment from 100 to up to 150 to account for any potential issues with sample quality and additional safety assessments.

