3.2 Protocol Map

3.3 Primary Outcomes

The primary outcome variables will be sensitivity and specificity of the cytosponge, as compared against the gold standard of the presence of EoE as detected by upper endoscopy with biopsies.

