6.2 Statistical Methods

Aim 1: To test the hypothesis that the Cytosponge accurately quantifies esophageal eosinophil counts in patients with active EoE, the maximum eosinophil counts from the Cytosponge and endoscopic biopsy will be compared by calculating the Pearson coefficient of correlation. In addition, patients will be categorized as having an eosinophil count either above or below 15 eos/hpf (the current diagnostic threshold). Agreement between patients above and below this threshold for Cytosponge and endoscopic biopsy will be measured using the kappa statistic. If eosinophil counts are not normally distributed, non-parametric methods will be used. Separate analyses will be performed for patients with active EoE and patients undergoing treatment.

Aim 2: Summary statistics will be calculated to describe adverse events and the tolerability of the Cytosponge. The proportion of subjects who prefer the Cytosponge will be calculated.

We predict that the Cytosponge will be safe and well-tolerated in patients with EoE, and that they will prefer this minimally invasive method to endoscopy with biopsy. We also predict that the eosinophil counts obtained with Cytosponge will strongly correlate with the counts from endoscopy with biopsy in both patients with active EoE.

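### The plan expects sample-quality problems but has no rule for a retrieved sponge without a usable count, so the primary sensitivity and specificity may by default describe readable sponges only

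*Combined protocol and SAP*

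**What the plan says.** Four places in the combined protocol and SAP bear on this.

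- **Section 3.3 (Primary Outcomes):** "The primary outcome variables will be sensitivity and specificity of the cytosponge", judged against EoE as found by endoscopy with biopsies.
- **Section 6.1 (Sample Size Determination):** the power statement begins "With 60 subjects enrolled for Aim 1" and concerns a correlation and a kappa. The section then permits "enrollment up to 150 subjects across both sites to account for any potential issues with sample quality", and names further safety assessment as a second purpose. It gives two reasons for the ceiling and does not divide the extra subjects between them.
- **Section 6.2 (Statistical Methods):** for the agreement analysis, "patients will be categorized as having an eosinophil count either above or below 15 eos/hpf". This is the only classification of a sponge result in the plan. Section 6.2 does not set out a separate analysis of sensitivity and specificity.
- **Section 6.3 (Subject Population for Analysis):** the population is all enrolled subjects who completed sponge administration and have pathology from the endoscopy that followed. It does not require the sponge to be readable.

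No section defines an adequate sponge sample, says how an inadequate one enters the primary analysis, or asks for the inadequate rate to be reported. The one test failure with a written consequence is failure to swallow: under Sections 4.4 and 5.1.3 those subjects are discontinued, which puts them outside the Section 6.3 population.

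**The concern.** Sections 6.2 and 6.3 do not fit together for one kind of subject: a person who swallowed the sponge, had it retrieved, had biopsies read, and whose sponge yields no usable eosinophil count. Section 6.3 includes that subject, and Section 6.2 has no result to assign. The analyst must do something, and the plan does not say what. If the choice is left until results are in hand, the denominator of the primary outcome is settled after the fact.

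The easy choice is also the favourable one. Leaving the subject out of the two-by-two table gives accuracy conditional on a readable sample. Sections 1.2 and 1.3 motivate the sponge as a way to cut down on endoscopies. For that use a sponge that cannot be read has not done its job, because the patient still needs the endoscopy. Readable-only accuracy answers an easier question. If readability is related to disease state, the readable-only figures may also be biased.

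**Working it through.** **The plan's own figure.** Inputs from Section 6.1: N = 60, R = 0.40, "with a power of 0.9 and an alpha of 0.05"; sidedness is not stated. By Fisher's z, power = Φ(atanh(0.40) × √(60 − 3) − 1.96) = Φ(0.4236 × 7.550 − 1.96) = Φ(1.24) = 0.892 two-sided, which reproduces the stated 0.9. This matters here for one reason: both the correlation and the kappa need a sponge result as well as a biopsy result. A subject without a sponge count adds nothing to either. Enrolling more people to cover sample quality therefore makes sense only if poor samples are expected to fall out of the count-based analyses. That is the basis for inferring the default; it is not a stated rule.

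**The unclassifiable subject, section by section.**
- Section 6.3: administration completed, yes; biopsy pathology available, yes. In the population.
- Section 6.2: above 15, unknown; below 15, unknown. No category.
- Section 3.3: sensitivity and specificity need a positive or negative sponge result. No cell.

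**Size, as an illustration.** Inputs:
- Sensitivity 100% and specificity 70% among readable sponges, borrowed from the pilot of 20 patients in Section 1.3.
- Unreadable share u, which the documents do not give. It is an assumption, taken as equal in biopsy-positive and biopsy-negative subjects.

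Formulas for the three possible scoring rules:
- Excluded: Se and Sp unchanged.
- Counted as a failure in both groups: Se × (1 − u) and Sp × (1 − u).
- Scored as negative: Se × (1 − u) and Sp × (1 − u) + u.

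| u (assumed) | Excluded, Se/Sp | Failure, Se/Sp | Scored negative, Se/Sp |
|---|---|---|---|
| 0% | 100% / 70% | 100% / 70% | 100% / 70% |
| 5% | 100% / 70% | 95% / 66.5% | 95% / 71.5% |
| 10% | 100% / 70% | 90% / 63% | 90% / 73% |
| 20% | 100% / 70% | 80% / 56% | 80% / 76% |

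For u = 10%: 1.00 × 0.90 = 0.90; 0.70 × 0.90 = 0.63; 0.63 + 0.10 = 0.73. At that rate the unwritten scoring choice moves sensitivity by 10 points (100% to 90%) and specificity across a range of 10 points (63% to 73%).

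**The case against.** The strongest reply is that the documents nowhere say unreadable sponges are excluded, and that Section 6.3 read literally keeps those subjects. That is correct, and it limits the point to a missing rule with a likely default. It does not remove the point, because Section 6.3 admits subjects whom Section 6.2 cannot classify.

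A reader might go further and infer that unreadable sponges are replaced by new subjects. The documents do not support this. Section 6.1 sets a ceiling and names no replacement. The only replacement rule, in Section 4.4, says that subjects who withdraw after the initial sponge are not replaced, and it does not deal with sample quality at all.

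A reader might also set 150 against 60 and infer that the plan tolerates losing 90 of 150 samples. That does not follow either, since the ceiling also serves additional safety assessments and no split is given.

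Other objections stand in part:
- Section 6.1 speaks of sample quality without naming the sponge, and Section 3.1 applies the term tissue samples to both methods.
- The 15 eos/hpf split is written for kappa. It is, however, the only sponge classification the plan has.
- With no adequacy threshold, a scanty sample could simply give a low count and be scored below 15. It would then lower sensitivity and raise specificity, so for specificity the direction is not fixed.
- Aim 1 is accuracy in quantifying eosinophils, and accuracy among evaluable samples is a legitimate target for that. This is a reason to keep the readable-only pair, not to report it alone.
- The pilot calls its samples adequate. It reports no count of inadequate ones, so it cannot supply u. Even if it meant 0 of 20, the exact two-sided 95% upper limit would be 1 − 0.025^(1/20) = 16.8%.

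**Conclusion.** The concern holds as a gap between Sections 6.2 and 6.3 that affects the primary outcome. The plan foresees sample-quality problems, includes subjects with unreadable sponges in its analysis population, and gives no way to score them. The likely default is to drop them, in which case the primary sensitivity and specificity describe readable sponges only. That default is inferred from how Sections 6.1 and 6.2 work together.

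The size depends on a rate that the documents do not report. Against a count-as-failure analysis, and on the pilot's 100%/70%, the readable-only figures would be higher by 5 and 3.5 points at an assumed 5% rate, 10 and 7 points at 10%, and 20 and 14 points at 20%. They would not differ at 0%. These figures assume equal rates in both biopsy groups. If unreadable were scored negative, the readable-only specificity would be the lower one. The documents do not show that accuracy will be overstated, only that nothing in the plan prevents it.

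**What to change.** In Sections 6.2 and 6.3:

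- Define an adequate sponge sample before sponge and biopsy results are unmasked and linked.
- Add non-diagnostic as a third sponge result.
- Report the non-diagnostic rate with an exact 95% confidence interval over all retrieved sponges, overall and by biopsy status.
- Report sensitivity and specificity twice: among readable sponges, and over the full Section 6.3 population with non-diagnostic counted as a failure in both groups (not detected if biopsy-positive, not cleared if biopsy-negative).
- Have any statement that the sponge can reduce the need for endoscopy cite the second pair.

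This needs no new subjects or procedures, and it works under either reading of Section 6.3. The cost is wording, one extra table, and a second accuracy figure that will be somewhat less favourable if any sponges prove unreadable.

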6.2 Statistical Methods

Aim 1: To test the hypothesis that the Cytosponge accurately quantifies esophageal eosinophil counts in patients with active EoE, the maximum eosinophil counts from the Cytosponge and endoscopic biopsy will be compared by calculating the Pearson coefficient of correlation. In addition, patients will be categorized as having an eosinophil count either above or below 15 eos/hpf (the current diagnostic threshold). Agreement between patients above and below this threshold for Cytosponge and endoscopic biopsy will be measured using the kappa statistic. If eosinophil counts are not normally distributed, non-parametric methods will be used. Separate analyses will be performed for patients with active EoE and patients undergoing treatment.

Aim 2: Summary statistics will be calculated to describe adverse events and the tolerability of the Cytosponge. The proportion of subjects who prefer the Cytosponge will be calculated.

We predict that the Cytosponge will be safe and well-tolerated in patients with EoE, and that they will prefer this minimally invasive method to endoscopy with biopsy. We also predict that the eosinophil counts obtained with Cytosponge will strongly correlate with the counts from endoscopy with biopsy in both patients with active EoE.

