IRB	Institutional Review Board
VAS	Visual Analog Scale

Study Summary

Title	Diagnosis and monitoring of eosinophilic esophagitis using the Cytosponge
Methodology	This will be a prospective cohort study, with patient enrollment conducted at UNC and Mayo Clinic by Drs. [name] and [name], and further sample analysis performed by [name]. In Aim 1, patients with eosinophilic esophagitis (EoE) or suspected EoE will be enrolled, tissue will be obtained from both the Cytosponge and routine care endoscopy, and the methods will be compared for a single time point to determine accuracy of Cytosponge for quantifying esophageal eosinophil counts. The patients who are being treated will be followed and tissue will be assessed over time with both Cytosponge and routine care endoscopy to determine the utility of Cytosponge for monitoring treatment response in patients with EoE. For all patients, safety will be monitored and subjects will complete a survey about the acceptability of Cytosponge (Aim 2).
Study Duration	2 Years
Study Center(s)	University of North Carolina, Chapel Hill, NC Mayo Clinic, Rochester MN
Objectives	
Aim 1: To determine the accuracy of Cytosponge for quantifying esophageal eosinophil counts in patients with active EoE, as compared to endoscopy with biopsy as the gold standard.
 
Aim 2: To determine the safety and acceptability of Cytosponge for patients with EoE.

Number of Subjects	150

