- Have a history of esophageal stricture that precludes passage of an adult endoscope,
- Have any history of esophageal varices, liver impairment of moderate or worse severity (Child's-Pugh class B & C), or evidence of varices noted on any past endoscopy,
- Have any history of esophageal surgery (except uncomplicated fundoplication), and history of coagulopathy, with INR >1.3 and/or platelet count of <75,000.

Cytosponge administration will occur after an overnight fast to minimize the possibility of aspiration of any gastric contents. Every administered sponge will be assessed post-procedure for signs of fracture or incomplete retrieval of the sponge. In the unlikely case of incomplete retrieval, the sponge will be retrieved with a Roth net at the standard of care endoscopy which will routinely immediately follow the administration of the sponge per the study protocol. Any bleeding noted, either clinically following the sponge administration or due to blood on the sponge itself, will be similarly investigated, and, as necessary, treated during the subsequent endoscopy. Because study inclusion/exclusion criteria are designed to exclude those at highest risk for a bleeding complication, the risk of bleeding in this study should be extremely low.

2 Study Objectives

Aim 1: To determine the accuracy of Cytosponge for quantifying esophageal eosinophil counts in patients with active EoE, as compared to endoscopy with biopsy as the gold standard.

Aim 2: To determine the safety and acceptability of Cytosponge for patients with EoE, all patients who are enrolled in both Aims 1 and 2 will be monitored.

3 Study Design

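### Section 6.2 uses a correlation as the first test of accurate quantification, and no named analysis estimates how far Cytosponge counts differ from biopsy counts

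*Combined protocol and SAP*

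**What the plan says.** Section 2 states Aim 1 as "To determine the accuracy of Cytosponge for quantifying esophageal eosinophil counts in patients with active EoE", with biopsy as the gold standard. The Methodology row of the Study Summary says that "the methods will be compared for a single time point to determine accuracy of Cytosponge for quantifying esophageal eosinophil counts".

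Section 6.2 opens its Aim 1 paragraph with "To test the hypothesis that the Cytosponge accurately quantifies esophageal eosinophil counts in patients with active EoE", and the first method it names is that "the maximum eosinophil counts from the Cytosponge and endoscopic biopsy will be compared by calculating the Pearson coefficient of correlation". The Study Summary repeats this. Section 6.2 then adds kappa on counts split at 15 eos/hpf and an unnamed non-parametric fallback for non-normal counts. It also says: "Separate analyses will be performed for patients with active EoE and patients undergoing treatment". Its closing prediction is "We also predict that the eosinophil counts obtained with Cytosponge will strongly correlate with the counts from endoscopy with biopsy".

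Section 6.1 gives 60 subjects for Aim 1. It says "we will be able to detect a correlation between the Cytosponge and endoscopy eosinophil counts" down to R = 0.40 with power 0.9 at alpha 0.05, and it gives a second justification based on kappa (0.7 against a null of 0.4, power 0.8).

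The correlation is not a listed outcome. Section 3.3 says "The primary outcome variables will be sensitivity and specificity of the cytosponge", and Section 3.4 lists kappa as the agreement outcome. The protocol nowhere plans a paired difference, a ratio, limits of agreement or a concordance coefficient for the two counts.

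**The concern.** Accurate quantification is a statement about how close two numbers are. A correlation measures how well they line up, whatever the slope or offset. A sponge that read twice the biopsy value in every patient would have the same r as one with no bias.

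Because 6.2 ties the correlation to the accuracy hypothesis and predicts a strong one, a high r could be reported as support for accurate quantification while the counts were systematically wrong. The remaining accuracy measures are binary, so a reader of the results could learn how well the sponge classifies patients at 15 eos/hpf, but not by how many eos/hpf, or by what factor, its counts differ from biopsy. The central hypothesis in Section 1.2 also covers monitoring of tissue eosinophilia during treatment, where the count level itself may be of interest.

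**Working it through.** **1. The plan's own figure.** Inputs from 6.1: n = 60, R = 0.40, alpha 0.05. Assumed, because not stated: null correlation 0, two-sided test. By Fisher's z, power = Φ(atanh(0.40) × √57 − 1.960) = Φ(0.4236 × 7.550 − 1.960) = Φ(1.238) = 0.892. The stated 0.9 reproduces. It is power to show an association; R = 0.40 corresponds to 0.40² = 16% shared variance.

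**2. What the correlation cannot see.** Let B be the biopsy count, S the sponge count and S′ = a + cS with c > 0. Then cov(B, S′) = c·cov(B, S) and SD(S′) = c·SD(S), so r is unchanged. The mean paired difference becomes a + c·mean(S) − mean(B), which does change. A rank correlation, the natural reading of the fallback, is unchanged under any strictly increasing distortion of S.

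**3. What the binary measures can see.** Kappa depends only on which side of 15 eos/hpf each count falls. Section 3.3 gives no cut for sensitivity and specificity; I take it to be the same 15. Any distortion that keeps every sponge count on its own side of 15 leaves all three exactly as they were.

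**4. Illustration.** The documents give no count distribution. Assumed: 60% of patients log-normal with biopsy median 45 eos/hpf and log-SD 0.7; 40% with median 4 and log-SD 1.0; sponge = biopsy × factor × log-normal noise with SD 0.35; 2,000,000 draws. About 60.2% have biopsy at or above 15, so 60 patients contain about 36 positives and 24 negatives.

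*Uniform over-counting (direction shows, size does not):*

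| Factor | r | Kappa | Sensitivity | Specificity | Exact 95% CI for specificity, 24 negatives |
|---|---|---|---|---|---|
| 1 | 0.903 | 0.90 | 95.2% | 94.7% | – |
| 1.5 | 0.903 | 0.86 | 99.3% | 84.2% | 63–95% (20/24) |
| 2 | 0.903 | 0.78 | 99.9% | 74.3% | 53–90% (18/24) |
| 3 | 0.903 | 0.63 | 100% | 59.0% | 37–78% (14/24) |

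The intervals overlap, and a specificity converts to a factor only if the distribution of counts below 15 is known. A paired analysis gives the size directly: at factor 2 the mean difference is +41.8 eos/hpf (approximate 95% CI at n = 60: 25 to 59) and the median is +18.4.

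*Bias away from the cut:*

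| Part of sponge count above 30 | r | Spearman | Sensitivity / specificity / kappa | Mean difference, all | Mean difference, biopsy ≥ 15 |
|---|---|---|---|---|---|
| Unaltered | 0.903 | 0.965 | 95.2% / 94.7% / 0.896 | +2.3 | +4 |
| Doubled | 0.887 | 0.965 | unchanged | +23.1 | +38 |
| Halved | 0.912 | 0.965 | unchanged | −8.1 | −14 |

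Halving the excess raises r slightly. Not every distortion behaves this way: capping sponge counts at 60 is not strictly increasing, and it lowers r from 0.90 to 0.77 and Spearman from 0.965 to about 0.96.

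**5. Precision of a paired analysis.** The 95% CI half-width, in SDs of the paired difference, is t/√n for the mean and t·√(1/n + 1.96²/(2(n−1))) for each limit of agreement. With n = 60 and t = 2.001 these are 0.26 and 0.44; with n = 150 they are 0.16 and 0.28. If the SD of the log ratio lies between 0.5 and 1.5 (assumed), n = 60 fixes the mean ratio to within a factor of exp(0.258 × 0.5) = 1.14 to exp(0.258 × 1.5) = 1.47.

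**6. Choice of scale.** With skewed counts the raw mean misleads: a sponge with no median bias but noise SD 0.7 has a mean difference of +10 and a median of 0. The median also has limits: with the excess above 30 doubled it is +1.0 overall and +13.3 when biopsy is at or above 15, so a plot against count level is needed. A log(count + 1) analysis returns a true factor of 2 as 1.89 overall, 1.98 at or above 15 and 1.76 below 15.

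**The case against.** The strongest reply is that this concerns a supporting analysis. The primary outcome is diagnostic classification, the listed agreement outcome is kappa, and 6.1 sizes the study on kappa as well as on the correlation. The only count threshold in the documents is 15 eos/hpf, no tolerated difference in eos/hpf is given, and the current Section 2 has no separate monitoring aim. All of that stands and limits the weight of the point. It does not remove it: Aim 1 and the 6.2 hypothesis are worded as quantification, and treated patients still have their own analysis in 6.2.

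A second reply is that the unnamed non-parametric methods might include a paired test. They might, though the sentence follows a correlation and a kappa. A test alone would not give limits of agreement, and no estimate of size is stated.

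Three stronger readings are tempting, and the documents do not support them.

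- *That bias would be invisible to this plan.* Sensitivity and specificity show bias across the cut and its direction. In the illustration, a doubled sponge (sensitivity 99.9%, specificity 74%, r 0.90) looks quite different from an unbiased but noisier one (89%, 90%, r 0.69).
- *That over-counting must go undetected in the active-EoE analysis.* That follows only if active EoE means a biopsy count of at least 15 eos/hpf, and the documents do not define the term. Patients with suspected EoE are eligible, so the overall population can include biopsy negatives.
- *That the sponge over-counts.* The pilot's 100% sensitivity and 70% specificity in 20 patients (Section 1.3) are compatible with over-counting but do not establish it.

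**Conclusion.** The concern holds in this form: the only named analysis of the counts as numbers measures association, so the plan has no named estimate of how far sponge counts differ from biopsy counts. The invariance of r to scale and shift, the invariance of a rank correlation to strictly increasing distortion, and the blindness of the binary measures to changes on one side of the cut are algebra and need no assumptions. The simulated sizes depend on assumed distributions, noise and bias; they show what could happen, not what is likely.

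The stated correlation power is correct for what it describes, and a reader should not infer that the primary outcome is invalid. The point merits a change because the stated hypothesis and the stated method do not match, and the remedy needs no new data.

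**What to change.** In 6.2 and in the matching Statistical Methodology row of the Study Summary:

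1. Describe the Pearson or rank correlation as a measure of association, not as the test of accurate quantification.
2. Add a paired agreement analysis of the two counts in eos/hpf: bias with a 95% CI, 95% limits of agreement, and a plot of the differences against count level.
3. Do not rely on the raw mean difference alone. Report the median paired difference and, if the spread grows with the count, a log or ratio-scale analysis with a stated rule for zero counts.
4. Report it overall and for the two groups that 6.2 already separates, saying how patients are assigned to each. Use one pair per patient or a method that allows for repeated pairs, because Section 5.3 permits up to 6 time points.
5. Keep sensitivity, specificity and kappa as planned.

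The cost is a few lines of text, one extra analysis of data already collected, and a more restrained reading of a high correlation. The primary outcome, sample size and procedures do not change.
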